We are currently studying SGB effects in postmenopausal women in a sham-controlled clinical trial funded by the National Institute on Aging (NIA R01AG049924-01; PI [name]).

Given the frequency and severity and interference of HF in men on ADT for prostate cancer, in addition to the negative effects HF impose on this patient population and a paucity of effective treatments, finding alternative treatments for HF in this population is needed.

STU#:00208657

Version 3.1

11/25/2019

3.0 STUDY ENDPOINTS:

Primary Outcome

Change in frequency of weekly hot flashes by self-report hot flash diary between baseline and 3 months following the intervention.

Secondary Outcomes

1. Change in frequency of weekly hot flashes by self-report hot flash diary between baseline and 1 month following the intervention.
2. Change in frequency of weekly hot flashes by self-report hot flash diary between baseline and 6 months following the intervention.
3. the change in hot flash severity (hot flash frequency * hot flash intensity) between baseline and 1, 3, 6 months following the intervention
4. the change in Hot Flash Related Daily Interference Scale (HFRDIS) between baseline and 1, 3, 6 months following the intervention
5. PROMIS SF4a (sleep)
6. Patient Global Impression of Change Score (PGIC)
7. Number and type of adverse events related to SGB according to NCI-CTCAE v5.0.

Mean frequency= $((F_{mi}+F_{mo}+F_{se})/7)$

where F_{mi} , F_{mo} and F_{se} are the weekly total number of mild, moderate or severe/very severe HF events

Mean severity = $(F_{mi}+2\times F_{mo}+3\times F_{se})/7$

where F_{mi} , F_{mo} and F_{se} are the weekly total number of mild, moderate or severe/very severe HF events In the case of mean severity, frequency of mild vasomotor symptoms (VMS) is not counted at baseline

4.0 STUDY INTERVENTION:

Image Guided Right Sided Stellate Ganglion Block with 0.5% Bupivacaine

5.0 PROCEDURES INVOLVED:

5.1 Study design:

We aim to conduct a single-site, open label trial of SGB in men with prostate cancer on ADT.

5.2 Methods & Study Procedures:

Refer to the Section 5.3, Schedule of Events, for additional information.

Visit 1

Consent

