After participants have reviewed and signed the consent form in person, they will be interviewed to determine candidacy for the study. They will be asked to provide information about themselves and their medical history. Participants will consult with [name] who will explain the injection procedure and perform a brief physical examination (focus on cervical range of motion and anterior cervical anatomy) to confirm patient eligibility for the

[name], MD STU00208657

V 3.1 11/25/2019

STU#:00208657

Version 3.1

11/25/2019

study. The SGB will be scheduled within 2 weeks of this visit, based on convenience and availability of the participant. Participants will be asked to complete a Hot Flash Related Daily Interference Scale and secondary outcome measures at this visit. They will complete a hot flash diary for at least 1 week. To qualify for study inclusion, participants must have ≥ 28 hot flashes per week or will be considered a screen failure and will be excluded.

Visit 2

Intervention

Participants will be NPO for 6 hours prior to the intervention and will arrange transportation home. At the time of the injection procedure, an angiocatheter will be placed in the hand/arm for peripheral intravenous access as a safety precaution. Participants will be positioned supine in cervical extension on a procedure table in the fluoroscopy suite of the NMH Pain Clinic (Lavin 1400). The anterior neck will be prepped with chlorhexidine and draped in the standard sterile manner.

A right-sided SGB will be performed. Using fluoroscopic guidance, the C6 vertebra will be identified and the skin overlying the tubercle will be anesthetized using 2 mL of 1% lidocaine. Using digital pressure to laterally retract the carotid artery, a 22 g 1.5-inch needle will be placed to make contact with the anterolateral portion of the C6 vertebra and then retracted 1-2 mm and secured; contrast material (iopamidol 1-2 mL) will be injected with fluoroscopic guidance to confirm contrast dye spread in the prevertebral fascial plane and to rule out intravascular or intrathecal dye spread. 0.5% bupivacaine (5 mL) will be injected and the needle will be removed.

Monitoring after SGB

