	Screening and Baseline Assessments ⁷	Registration ⁷	Day of Intervention ⁸	1 day follow-up (+ 3 day window)	1 month follow-up (± 7 day window)	3 month follow-up (± 7 day window)	6 month follow-up (± 7 day window)
Informed consent	X						
Demographic information and medical history ¹	X						
Physical exam, height, and weight ²	X						
AE assessment ³	X		X	X	X		
HF severity assessments ⁵	X (collect HF data for ≥ 1 week prior to the day of intervention)				X	X	X
HFRDIS ⁶	X			Weekly during follow-up per Section 5.2			
PROMIS SF4a ⁶	X				X	X	X
PGIC score ⁶					X	X	X
Registration ⁷		X					
SGB Intervention ⁸			X				
Horner's sign assessment post-SGC intervention ⁸			X				
Timed vitals during recovery ⁹			X				
Follow-up contact ¹⁰				X	X	X	X
Weekly reminders ¹¹				X			
Hot flash diary ^{12, 5}				X			

STU#:00208657

Version 3.1

11/25/2019

1. Demographic information and medical history to include: age, body mass index, race, years of education, marital status, Gleason score, duration of hot flashes (months), type of ADT (specify) per Section 5.4. Height and weight to be collected for BMI calculation. Pathology report to be collected to determine Gleason Score.
2. Brief physician-directed physical exam to focus on cervical range of motion and anterior cervical anatomy per Section 5.2.
3. Refer to Section 5.6 for details on the collection of AEs and SAEs. In brief, AEs that are related to the intervention (irrespective of expectedness) will be collected from the time of consent (baseline) through the 30 days after the intervention (the 1 month follow-up visit). All SAEs (irrespective of attribution/relatedness or expectedness) will be collected from the time of consent (baseline) through 30 days after the intervention (the 1 month follow-up visit).
4. Screening labs not required for this study; not a standard of care
5. Patient-reported hot flash (HF) frequency and HF intensity to be collected, based on the participant's hot flash diary. These values will be used to calculate a HF severity score, per Section 3.0. Participants must complete the diary for at least 1 week prior to receipt of the intervention to be able to determine the baseline HF severity score.
6. HFRDIS, PROMIS SF4a, and PGIC score questionnaires to be administered via REDCap. Other methods may also be used (i.e. in person, over the phone, through mail or email, etc.) if required.

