7. All screening assessments to be conducted 0-14 days prior to registration, unless otherwise indicated. Participants must register to the trial prior to receipt of the study intervention. Refer to Section 12.0 for registration instructions.
8. The SGB intervention should take place AFTER registration and within 1-2 weeks after the baseline/screening assessments per Section 5.2. Participants are to complete the diary daily starting at least 1 week prior to receipt of the SGB intervention. Details of the SGB intervention and Horner's sign assessment are described in Section 5.2
9. Vitals are to be assessed approximately every 5 minutes for approximately 20-30 minutes while participants are in recovery, after receipt of SGB.
10. Participants will be contacted for follow-up via their preferred method of contact (phone call, in-person visit, email, etc.) 1 day and 1 month after the intervention to collect AE/SAE data. They will also be contacted (via REDcap or other means) at 1 month, 3 months, and 6 months to collect information for secondary outcomes.
11. Qualified research staff may contact participants via their preferred method of contact (phone call, in-person visit, email, REDcap generated email, etc.) approximately once a week (or less frequently as needed) throughout the course of the study to remind participants to comply with study procedures, including but not limited to: scheduling appointments; completing the HF diary; completing the HFRDIS, PROMIS SF4a, and PGIC score questionnaires; assessing AEs/SAEs.
12. Participants will be instructed to begin completing the hot flash diary at the time of screening/baseline assessments. Participants are to complete the diary daily starting at least 1 week prior to receipt of the SGB intervention and through the 6-month follow-up time point. Weekly phone calls (or other preferred method of contact) may be used to remind participants to comply.

STU#:00208657

Version 3.1

11/25/2019

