11.0 PARTICIPANT POPULATION

Accrual Number:	Category/Group: Adults	Consented: Maximum Number to be Consented or Reviewed/Collected/Screened	Enrolled: Number to Complete the Study or Needed to Address the Research Question
Total:	18	18	14

STU#:00208657

Version 3.1

11/25/2019

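### Qualifying diary days are not kept apart from baseline days, so in this single-arm trial a modest regression to the mean can be counted as SGB effect

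*Combined protocol and SAP*

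**What the plan says.** All references are to the combined protocol and SAP.

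- **Gate.** Section 5.2, Visit 1: "To qualify for study inclusion, participants must have ≥ 28 hot flashes per week". A man below this is a screen failure.
- **Start of diary.** Schedule of Events, footnote 12: "Participants will be instructed to begin completing the hot flash diary at the time of screening/baseline assessments". No diary before consent is described. The telephone pre-screen in Section 12.1 is a survey that includes the HFRDIS.
- **Source of baseline.** Schedule of Events, footnote 5, tells men to "complete the diary for at least 1 week prior to receipt of the intervention to be able to determine the baseline HF severity score". Footnotes 8 and 12 set the same minimum of one pre-SGB week.
- **Time to SGB.** Section 5.2: "The SGB will be scheduled within 2 weeks of this visit". Footnote 8 says "within 1-2 weeks after the baseline/screening assessments per Section 5.2" and places SGB after registration.
- **Design and test.** Section 5.1 describes a "single-site, open label trial of SGB in men with prostate cancer on ADT". The Statistical Plan in Section 17.0 tests follow-up against baseline within person, with no change as the null hypothesis.
- **Accrual.** Section 11.0, under "Consented: Maximum Number to be Consented or Reviewed/Collected/Screened", gives 18, with 14 to complete. The Study Summary and Section 17.0 explain the gap between 14 and 18 as dropout.

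No section says which diary days make up baseline weekly frequency, or requires a baseline week separate from the qualifying week.

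**The concern.** A man enters because his diary count reached the gate. Part of a high count is week-to-week variation, so a later week is expected to be lower even if SGB does nothing. If the qualifying days are also the baseline days, that fall sits inside the change from baseline. A randomised control arm would share it and cancel it; this design has none.

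The bias acts directly on all weekly flashes, which is the Section 3.0 primary outcome. It is weaker for severe flashes, which Section 17.0 analyses, because entry is on all flashes. No direction can be claimed for the severity score. Section 3.0 states "In the case of mean severity, frequency of mild vasomotor symptoms (VMS) is not counted at baseline", which lowers baseline and works the other way.

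At stake are the size of the reported reduction, the one-sided error rate of the p<0.05 test, and the later randomised trial, which Section 17.0 says may be designed from these data.

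**Working it through.** **1. The plan's own figure.** SD of change = √(SD1² + SD2² − 2ρ·SD1·SD2), with SD1 = 43 and SD2 = 21.

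- ρ = 0.8: √(1849 + 441 − 1444.8) = 29.07. With Δ = 23.9, exact paired-t power at n = 14 is 81.1%.
- ρ = 0.7: √(1849 + 441 − 1264.2) = 32.03. Power at n = 17 is 82.3%.
- 14/(1 − 0.2) = 17.5, rounded up to 18.

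All three reproduce. The sample size is not in dispute.

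**2. When gate and baseline coincide.** The diary starts at Visit 1. With SGB on day 7 there is only one diary week, so it is both. With SGB between days 8 and 13, a 7-day baseline ending at SGB shares days with the first week. Only at day 14 do two full separate weeks exist.

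**3. What pass rate the accrual table allows.**

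- All four spare men are screen failures: 14/18 = 78%. This leaves no dropout, so it is a floor on the pass rate.
- 90% pass: 16.2 men enter, and 14/16.2 = 86% must complete, leaving about 14% for dropout.
- The full 20% dropout is kept: 14/(18 × 0.8) = 97% must pass.

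A pass rate of 90% or more therefore fits the plan best.

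**4. Size with no treatment effect.** Assumptions: gamma-shaped weekly counts; CV 43/46, borrowed from severe flashes in Section 17.0; entry at 28 or more; Pearson ρ from the plan's range, applied before selection; n = 14; paired t-test, two-sided 0.05. The mean is set to give the stated pass rate. Simulated results:

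| Pass rate | Fall, ρ = 0.8 | Fall, ρ = 0.5 | Significant reduction, ρ = 0.8 | Significant reduction, ρ = 0.5 |
|---|---|---|---|---|
| 90% | 0.9% | 3.0% | 2.7% | 3.3% |
| 78% | 2.4% | 7.3% | 3.8% | 5.6% |
| 70% (mean 70) | 3.6% | 10.2% | 4.9% | 8.1% |
| 57% (mean 46) | 5.6% | 15.2% | 7.2% | 14.2% |

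The nominal rate for significant reductions is 2.5%. The last two rows lie below the 78% floor, so they apply only if the accrual table is optimistic.

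**5. Sensitivity.**

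- *Straight-line check.* Fall = (1 − ρ) × (mean of those enrolled − mean before selection). At 78% passing, 0.2 × (120.3 − 96.7) = 4.7, or 3.9% of 120.3; at ρ = 0.5 it is 11.8, or 9.8%. At 90% passing (means 232.4 and 210.6) it is 1.9% and 4.7%. This is somewhat above the simulation, but of the same order.
- *Count shape.* At 78% passing with the mean set to 46 or 60 and the CV reduced to fit, false significant reductions run from 4.6% to 7.9%. At 90% passing, other gamma shapes reach 4.6%.
- *Severe flashes*, 78% passing, assumed correlation with all flashes 0.5 to 0.9: fall 1.9% to 2.4% (ρ = 0.8) and 5.4% to 7.1% (ρ = 0.5).
- *Severity score.* Leaving out mild flashes lowers baseline by 0.10/(0.10 + 0.90 + 1.35) = 4.3% for an assumed 10/45/45 mix of mild, moderate and severe, and by (1/3)/(1/3 + 2/3 + 1) = 16.7% for equal thirds. The net direction depends on the mix.
- *The >35% threshold*, 78% passing: with no treatment effect, the observed fall exceeds it in 0.3% of trials at ρ = 0.8 and 6.4% at ρ = 0.5.

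**The case against.** The strongest case is that the point is immaterial. At ρ = 0.8, the value behind n = 14, the artefact is about 1% to 2.4%, against a >35% threshold, a 52% planning effect and a 13% fall in the sham arm of the sponsor's earlier trial in women. The study is called exploratory, and a sham-controlled trial is planned next. The telephone HFRDIS screen already selects affected men, so the diary gate probably excludes few. If ρ = 0.8 describes enrolled men, the fall is smaller still: a pre-selection 0.8 becomes about 0.75 among those enrolled at 78% passing. At 78% passing and ρ = 0.8, total two-sided rejections are about 5.1%, close to nominal. Coincidence is forced only at exactly one week, and registration must also fit in before SGB.

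Most of this stands and sets the weight of the point. It does not remove it. Nothing in the text prevents overlap, the errors lean towards benefit (3.8% reductions against 1.2% increases in that same case), and the baseline days need defining anyway.

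Three stronger readings are tempting, and the documents do not support them:

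- *That the plan prescribes one week for both purposes.* It leaves baseline days undefined; they coincide only when SGB is early.
- *That false significant reductions are inflated severalfold.* That needs pass rates below what Section 11.0 permits, or 46 ± 43 read as all flashes when Section 17.0 gives it for severe flashes.
- *That the 13% sham fall measures this artefact.* The documents do not attribute it to regression to the mean.

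**Conclusion.** The point holds as a minor one. The plan lets qualifying days serve as baseline days, and an uncontrolled test against zero change counts the resulting regression to the mean as SGB effect. Under the plan's accrual figures the expected fall without treatment is about 1% to 3% if nearly all consented men pass, and at most 2.4% to 7.3% at the 78% floor in the gamma model. The excess of false significant reductions is correspondingly small, up to about 8% of trials in the least favourable count shape at that floor.

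These sizes are illustrations. The documents give no pre-screening distribution of all weekly flashes, so the CV, the gamma shape and the use of ρ before selection are assumptions. A reader should not infer that the artefact could by itself account for a fall of 35% or 52%: at ρ = 0.8 it almost never reaches the threshold.

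**What to change.** - In Section 5.2 and Schedule of Events footnotes 5, 8 and 12, state that the first diary week is used for eligibility only, and that baseline weekly frequency comes from the 7 diary days immediately before SGB that do not overlap it.
- Reconcile the Visit 1-to-SGB timing and registration text in Section 5.2 and the footnotes so that this fits. In the same edit, reconcile the gate itself: Section 5.2 admits a count of exactly 28, and Section 9.0 requires more than 28.
- Where overlap cannot be avoided, flag the man and report a sensitivity analysis without those men.
- State that a separate week reduces regression to the mean, does not fully remove it if week-to-week correlation decays, and does not remove placebo response or natural course. Describe the result as an uncontrolled change when it is used to plan the later trial.

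**Cost:** up to one extra diary week for some men. Two full weeks fill the 14-day window with registration still to fit, so there is little scheduling slack.

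**Gain:** at 78% passing, if correlation is constant over time, the fall goes to about 0% and false significant reductions to 2.2% to 2.3%. If adjacent weeks correlate at an assumed 0.9, the fall drops only from 2.4% to 1.3% (ρ = 0.8) or from 7.3% to 6.2% (ρ = 0.5), and false significant reductions from 3.8% to 3.0% or from 5.6% to 4.9%.

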Study Title: Does Stellate Ganglion Blockade (SGB) in Men Treated for Prostate Cancer Improve Hot Flashes? A Pilot Prospective Cohort Study

Study Protocol Version 3.1 11/25 2019

NCT003796195

STU#:00208657

Version 3.1

11/25/2019

PROTOCOL TITLE: Does Stellate Ganglion Blockade (SGB) in Men Treated for Prostate Cancer Improve Hot Flashes? A Pilot Prospective Cohort Study

PRINCIPAL INVESTIGATOR:

[name], MSCI

Department of Anesthesiology

[contact]

[contact]

Co-Investigator

[name], MPH

Department of Medicine, Division of Hematology & Oncology

Statistician

[name]

Department of Anesthesiology

VERSION NUMBER:

3.1

VERSION DATE:

11/25/2019

STUDY SUMMARY:

Special Population(s)	NA
Sample Size	N = 14 is the required number of enrollees who are needed to be evaluable both at baseline and 6 months for the primary outcome. Allowing for dropouts, up to 18 pts might be enrolled
Funding Source	Internal funding
type of consent to be obtained	Written
Site	Single Site
Research Related Radiation Exposure	Yes

STU#:00208657

Version 3.1

11/25/2019

1.0 OBJECTIVES:

Scope: Men with prostate cancer with or without metastatic disease treated with androgen deprivation therapy for at least 2 months, with bothersome refractory hot flashes, will be enrolled as participants in this open label clinical trial.

Aim 1: To determine the effect of stellate ganglion blockade (SGB) for reducing hot flash frequency and severity in men with prostate cancer in the 6 months following the intervention.

Aim 2: To evaluate the effect of SGB on daily hot flash (HF) interference and sleep quality.

Hypotheses: Hot flash frequency, interference and sleep quality will be improved in men following stellate ganglion blockade with local anesthetic.

2.0 BACKGROUND:

Androgen Deprivation Therapy (ADT) is a critical component of advanced prostate cancer treatment but causes numerous adverse effects including decreased bone mass, decreased muscle mass, gynecomastia, erectile dysfunction, loss of sexual desire, depression, disordered sleep, urinary symptoms, and hot flashes (HF)(1). HF are unpleasant paroxysmal episodes of flushing, sweating with vasodilation of the face, neck, and chest. These episodes can last for seconds to minutes and are often associated with night sweats, anxiety, and insomnia and have negative effects on quality of life (9).

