Participants will be transferred to a recovery area and monitored in a reclining position for approximately 20-30 minutes after the SGB to assess potential adverse effects of the injection. Vital signs will be measured approximately every 5 minutes during the recovery phase. Presence of a Horner's sign (miosis, ptosis, anhydrosis) will be recorded and will validate successful SGB. Expected adverse events and serious adverse events may include any of the following:

Adverse Events (Immediate Post-Procedure):

Local anesthetic toxicity (seizure, loss of consciousness)

Inability to swallow (superior laryngeal nerve spread of local anesthetic)

Difficulty with phonation (recurrent laryngeal nerve spread of local anesthetic)

Weakness of arm (brachial plexus spread of local anesthetic)

Weakness of arms and legs (epidural spread of local anesthetic)

Shortness of breath (phrenic nerve spread of local anesthetic)

These effects would be clinically apparent in the Post-Anesthesia Care Unit (PACU) during the 30 minute post injection observation period; patients are not discharged until vital signs, motor and sensory function of the upper and lower extremities are assessed as normal, and patient is able to phonate and swallow liquids.

STU#:00208657

Version 3.1

11/25/2019

Follow-Up

- 24h follow-up (+3 days to allow for scheduling constraints with weekends)

Participants will be contacted one day following the intervention to assess for any adverse events or side effects. Expected adverse events may include any of the following:

Pain at injection site

Swelling at injection site

Severe bruising at injection site

- Long-term follow-up at 1, 3, and 6 months

Participants will complete daily hot flash diaries and weekly HFRDIS scales via REDcap email for the duration of the 6 month follow up. Secondary measures will be collected at 1, 3 and 6 months after the intervention. Participants will have the opportunity to share any new concerns or problems with research personnel during these interactions, and will be instructed to contact [name] (PI) if any more urgent concerns arise. Contact information is provided in the ICF.

Patients will be contacted via telephone or via REDcap generated email on a weekly basis, if needed, to encourage continued participation in follow up measures, and data will be collected via REDcap. Reminder phone calls will be made if the participant forgets to send their information.

Schedule of Events

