Nominal patient characteristics data will be summarized descriptively as number and percent of participants in each category. Ordinal and continuous patient data that are not approximately normally distributed will be summarized as median and interquartile range (IQR). Normally distributed continuous patient data will be presented as mean \pm SD.

STU#:00208657

Version 3.1

11/25/2019

Data required for the primary outcome variable, i.e., mean daily frequency of severe hot flashes in the study sample at 6 months after the intervention vs. the baseline daily frequency of hot flashes in the study sample, will be reported as the mean \pm SD if appropriate, or as the median (IQR) otherwise. The primary outcome data will be evaluated using a paired t-test if the data are approximately normally distributed, or using with the Wilcoxon matched pairs signed rank test if they are not. The mean difference and 95% CI will be calculated. The criterion for rejection of the null hypothesis (i.e. no change over the baseline to 6-month follow-up assessment of the mean weekly frequency of severe hot flashes) will be a two-tailed $p < 0.05$.

For AE analysis, safety and tolerability will be summarized descriptively by providing the frequency of adverse events by severity, type, and attribution.

Differences from baseline and associated 95% CIs will be calculated for planned analyses. Variables that are approximately normally distributed (e.g., hot flash frequency) will be summarized as mean \pm SD. These data at baseline, 1, 3, and 6 months will be compared using the one-way repeated measures analysis of variance with pairwise multiple comparison with baseline made using the Holm-Sidak method when appropriate.

The criterion for rejection of the null hypothesis for all of the secondary analyses will be a two-tailed $P < 0.05$, as this is an exploratory study.

With severe HF frequency selected as the primary outcome, $> 35\%$ reduction from baseline to 6 months will be considered to be clinically significant. However, as this is an exploratory study, a larger reduction was used for the power analysis presented above.

If this study shows meaningful treatment effects in this study population, we plan to further evaluate our hypotheses in a larger, randomized blinded sham controlled study.

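### A man lost before the primary time point drops out of the primary paired test despite his earlier daily diaries; a longitudinal analysis that keeps partial completers should be added

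*Combined protocol and SAP*

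**What the plan says.** **Collection.** Section 5.2 (Follow-Up): "Participants will complete daily hot flash diaries and weekly HFRDIS scales via REDcap email for the duration of the 6 month follow up". Note 12 to the Schedule of Events has the diary kept daily from at least a week before the block "through the 6-month follow-up time point".

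**Aim.** Aim 1 in Section 1.0 concerns the effect of the block "for reducing hot flash frequency and severity in men with prostate cancer in the 6 months following the intervention".

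**Endpoints.** Section 3.0 gives the primary outcome as "Change in frequency of weekly hot flashes by self-report hot flash diary between baseline and 3 months following the intervention", with months 1 and 6 as secondary. HFRDIS is collected weekly, but its endpoint is "the change in Hot Flash Related Daily Interference Scale (HFRDIS) between baseline and 1, 3, 6 months following the intervention".

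**Analysis.** The Statistical Plan in Section 17.0 puts the primary comparison at 6 months, for severe hot flashes: "The primary outcome data will be evaluated using a paired t-test if the data are approximately normally distributed", with the Wilcoxon signed rank test otherwise. For the time course: "These data at baseline, 1, 3, and 6 months will be compared using the one-way repeated measures analysis of variance", with Holm-Sidak comparisons against baseline.

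**Attrition.** The Study Summary requires 14 men with usable data at baseline and at 6 months. The Power Analysis expects losses of about 20% and recruits up to 18. No missing-data method, mixed model, weekly trajectory or period average is described.

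**The concern.** A paired test uses only men with both measurements. A man who keeps his diary for two or four months and then stops has given direct evidence on his response, but a 6-month paired test uses none of it. A classical repeated-measures ANOVA has the same difficulty, because it needs complete rows, and the plan does not say what happens to incomplete ones.

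Two things are at stake. One is precision, in a trial sized at 14. The other is bias. Section 14.0 allows withdrawal of men who do not supply outcome measures or who start a medication known to affect hot flashes. Either reason could go with a poor response, and the remaining men would then look better than the treated group. Section 17.0 wants this pilot to supply frequency and variability estimates for a larger randomised trial, so such a bias would carry forward.

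The diary weeks between visits are a lesser matter. They show when the effect of a single block begins and fades, which no planned analysis describes.

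**Working it through.** **Inputs.** From the Power Analysis in Section 17.0: baseline mean 46.0, SD1 = 43, SD2 = 21, ρ = 0.8 (alternative 0.7), Δ = 23.9, two-sided α = 0.05, n = 14, attrition about 20%. Assumed here: 6 months is about 26 weeks, follow-up weeks are equally correlated at r, and the effect is constant over follow-up.

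**1. The plan's own figures.** Var(change) = SD1² + SD2² − 2ρ·SD1·SD2 = 1849 + 441 − 1444.8 = 845.2, so SD = 29.07. Noncentrality at n = 14 is (23.9/29.07)·√14 = 3.08. With 13 df the exact paired-t power is 81.1%, and 14 is the smallest n reaching 80%. With ρ = 0.7 the variance is 2290 − 1264.2 = 1025.8, SD = 32.03, and n = 17 (power 82.3%). Attrition: 14/0.80 = 17.5, so 18. All stated figures reproduce.

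**2. Keeping all 18 men, still one follow-up week each.** Noncentrality is (23.9/29.07)·√18 = 3.49 and power is 90.7%. With ρ = 0.7, power goes from 73.3% (14 men) to 84.7% (18 men).

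**3. Adding weeks.** For the mean of k follow-up weeks, Var(change) = 1849 + 441·[1 + (k − 1)r]/k − 1444.8. For example, at r = 0.8, k = 26: 441 × 21/26 = 356.2, giving 760.4 and SD 27.58.

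| r | SD, k = 3 | SD, k = 26 | Power n = 14, k = 3 → 26 | Power n = 18, k = 3 → 26 |
|---|---|---|---|---|
| 0.80 | 28.04 | 27.58 | 83.8% → 85.0% | 92.6% → 93.4% |
| 0.90 | 28.56 | 28.33 | 82.5% → 83.1% | 91.7% → 92.1% |
| 0.95 | 28.82 | 28.71 | 81.8% → 82.1% | 91.2% → 91.4% |

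Going from three planned points to 26 weeks adds 0.3 to 1.2 points at n = 14 (1.8 at r = 0.7) and 0.2 to 0.8 at n = 18. The gain is small because the baseline variance of 1849 dominates and extra follow-up weeks do not reduce it.

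**4. Simulation with dropout** (2,000 runs per setting; 18 men; normal data; r = 0.7, 0.8, 0.9; ρ = 0.8; true change −23.9). Four men stop at a random week from 3 to 20. The longitudinal estimates use generalised least squares with the covariance known, which flatters them.

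| | Completers, week 26 | Longitudinal, months 1/3/6 | Longitudinal, weekly |
|---|---|---|---|
| Dropout at random: SD of month-6 estimate | 7.74 to 7.84 | 6.99 to 7.06 | 6.94 to 7.06 |
| Four worst early responders leave: mean change | −33.2 to −34.0 | −24.1 to −24.2 | −23.8 to −23.9 |

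For comparison, 29.07/√14 = 7.77 and 29.07/√18 = 6.85, so the longitudinal estimate recovers most of the lost precision but not all. Under dropout at random, completer power is 80.7% to 81.8%. A t-test on per-man mean change has power 90.7% to 92.6% from the three visits and 91.8% to 94.8% from all weeks. Under selective dropout, completers overstate the benefit by 9.3 to 10.1 hot flashes a week (33.2 − 23.9 and 34.0 − 23.9). That scenario is deliberately extreme.

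**5. Choice of model.** A plain random-intercept model with baseline as an outcome row forces equal variance and equal correlation before and after treatment, while the plan assumes SDs of 43 and 21. In two simulations on those SDs, its 95% interval for the average change covered the truth about 56% and 59% of the time at r = 0.8, and 44% and 48% at r = 0.9. A paired t-test on per-man mean change covered about 93% to 98%.

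**The case against.** Several objections have force.

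- **The extra weeks barely matter for power.** This stands. A reader might infer that power of 91% to 93% comes from analysing 26 weeks of diary. It does not: 18 men with a single follow-up week already reach 90.7%. A likelihood model on months 1, 3 and 6 also removes nearly all the simulated dropout bias.
- **Nothing is being discarded.** A reader might infer that the plan throws diary data away. No text says so; the diary supplies the weekly totals at each visit. What is true is that no analysis is named for the other weeks.
- **Aim 1 does not state a period average.** A reader might take its wording as defining one. It names no average, and Section 3.0 puts it into practice as change at 1, 3 and 6 months. An average over follow-up is a reasonable supplementary summary, not the estimand that the documents fix.
- **Who is lost depends on the primary time point.** Under Section 3.0, a man lost after month 3 contributes fully to the primary comparison. Under the Study Summary and Section 17.0 he does not. The conflict must be settled first.
- **The power figures assume a constant effect.** If the effect builds or wanes, the average is a different quantity and the comparison no longer applies. This stands as a limit on the numbers.
- **This is a small, exploratory, uncontrolled pilot.** True, and no longitudinal model supplies a control group. But a pilot meant to inform a larger trial gains from using every treated man, at almost no cost.

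**Conclusion.** The concern holds as an inexpensive improvement to the analysis plan. The sample size is not in error. The gap is that the primary analysis is confined to men measured at the primary time point, with no missing-data method and attrition handled only by over-recruiting.

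Keeping partial completers would raise power from about 81% to at most about 91%. That upper figure rests on the plan's SDs, ρ = 0.8, a constant effect, and dropouts being nearly as informative as completers. The weeks beyond months 1, 3 and 6 add about 1 point; their main use is to describe onset and waning. Protection against selective dropout may matter more than power, but it depends on data being missing at random given what was recorded. Men with no follow-up diary still contribute no change.

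**What to change.** 1. Reconcile the primary time point (3 or 6 months) and measure (all or severe hot flashes) between Section 3.0, the Study Summary and Section 17.0. Define the diary week for each time point and the minimum number of diary days.
2. Keep the time-point comparisons. Pre-specify one likelihood-based longitudinal analysis of every treated man with a baseline and any follow-up diary.
3. Let variances and correlations differ between baseline and follow-up. One option is an unstructured mixed model on baseline and months 1, 3 and 6, replacing the repeated-measures ANOVA. Another is weekly change from baseline with baseline as a covariate. Use small-sample or robust standard errors. Do not use a plain random-intercept model with baseline as an outcome row.
4. Report the 1-, 3- and 6-month contrasts with 95% intervals. As a supplementary summary for Aim 1, report the per-man average change over follow-up and plot the weekly course.

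Cost: a paragraph in Section 17.0 and some analysis code, with no new data. The downside is reliance on missing-at-random and covariance assumptions, which 14 to 18 men can check only weakly.
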